6.2.2 Secondary Efficacy Analysis

6.2.2.1 Secondary efficacy endpoints

The secondary efficacy variables are specified below.

- Overall survival
- Time to first SSE
- Radiological progression-free Survival (rPFS)
- Time to radiological progression (TTP)
- Pain improvement rate
- Time to pain progression

Overall survival is defined for each comparison as the time (days) from the applicable start date to the date of death due to any cause. See [Table 9–3](#) in Appendix 9.1.2 for detailed censoring rules.

Comparison 1:

Arm C subjects who have died or are known to be alive after ‘pooling cut-off date’ will be censored on the ‘pooling cut-off’ date. Refer to Section 4.5 for pooling cut-off date.

All other subjects in arms A, B and C, refer to [Table 9–3](#) for censoring rules.

Overall Survival (OS) following randomization = End Date – Date of Randomization +1

Comparison 2:

For Comparison 2 eligible subjects, refer to [Table 9–3](#) for censoring rules.

Overall Survival (OS) following Week 24 baseline = End Date – Date of Week 24 baseline(the 6th dose date) +1

Time to first symptomatic skeletal event is defined for each comparison as the time (days) from the applicable start date to the date of the first SSE. See

[Table 9–4](#) in Appendix 9.1.3 for detailed censoring.

Time to radiological progression is defined for each comparison as the time (days) from the randomization date to the date of the first radiological progression. Comparison 2 will not follow the Week-24 baseline and randomization baseline will be used instead. See [Table 9–5](#) and [Table 9–6](#) in Appendix 9.1.4 for detailed censoring rules.

The central reviewer will evaluate the radiological imaging produced by the investigator. Primary radiological progression endpoints will be based on the central radiological reviewer assessments. Investigator assessments will be provided as a sensitivity analysis.

Radiological progression of soft-tissue disease is determined according to modified RECIST criteria, version 1.1 (See Protocol Section 14.1) based on MRI / CT scans of the chest, abdomen, and pelvis.

Radiological progression of bone disease is determined according to adapted PCWG2 criteria (see Protocol Section 14.2) based on whole body technetium-99 bone scans.

Radiological progression of bone disease requires confirmation. A subject is considered to have progressed by bone scan if:

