- The first bone scan with ≥ 2 new lesions compared to baseline is observed < 12 weeks from randomization and is confirmed by a second bone scan taken ≥ 6 weeks later showing ≥ 2 additional new lesions (a total of ≥ 4 new lesions compared to baseline); or
- The first bone scan with ≥ 2 new lesions compared to baseline is observed ≥ 12 weeks from randomization and the new lesions are verified on the next bone scan ≥ 6 weeks later (a total of ≥ 2 new lesions compared to baseline).

The date of progression of bone disease will be the date of the first observed bone progression, not the date that confirmed the bone progression.

The date of radiological progression will be determined following the rules in [Table 9–6](#).

Radiological progression-free survival is defined for each comparison as the time (days) from the randomization baseline to the date of radiological disease progression or death from any cause (if death occurs without prior progression). See [Table 9–7](#) in Appendix 9.1.5 for detailed censoring rules for both Comparison 1 and Comparison 2.

If data permits, unconfirmed radiological progression-free survival and time to unconfirmed radiological progression will be analyzed as sensitivity analyses based on central reviewer. Bone progression in this case does not require confirmation.

Pain endpoints

The pain data collected from ePRO will be used for these analyses.

Worst pain score (WPS) at a given visit is defined for each subject as the mean of the 7 day “worst pain score” assessments taken on or before each applicable visit. If less than 4 non-

missing WPS values are available for a given visit, then the weekly worst pain score will be left missing for that visit.

Timepoint pain improvement rate is defined with respect to each applicable baseline as the proportion of subjects with a 30% and 2-point decrease in WPS with respect to the applicable baseline assessment over 2 consecutive assessment periods conducted at least 3 weeks apart among subjects with a WPS score ≥ 4 at the applicable baseline. The first of the 2 consecutive periods is taken to be the date of improvement.

Time to pain progression is defined for each comparison in subjects with a WPS of ≤ 7 at the applicable baseline as the time from the applicable start date to an increase of 2 or more points in WPS (with respect to the applicable baseline). Refer to

Table 9–4 in Appendix 9.1.3 for detailed censoring rules.

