6.2.3.1 Exploratory endpoints

The exploratory variables are specified below:

- Time to radiological bone progression
- Time to radiological soft-tissue progression
- Patient bone scan lesion area (BSLA)
- Patient bone scan time point response rate (week 8, week 16 and week 24) and best overall response rate, based on central review
- Total alkaline phosphatase (ALP) response rate
- Time to total alkaline phosphatase (ALP) progression
- Time to total alkaline phosphatase (ALP) progression without 12 week restriction
- Percentage change in total alkaline phosphatase (ALP) at 12 and 24 weeks
- Prostate specific antigen (PSA) response rate
- Time to PSA progression
- Time to PSA progression without 12 week restriction
- Pain improvement rate without increase in analgesic use (week 12, week 24, EOT and overall)
- Time to pain progression or increase in analgesic use
- Change in analgesic use
- Time to increase in analgesic use
- NCCN-FACT FPSI-17 subscale scores
 - FPSI Disease Related Symptoms – Physical (DRS-P)
 - FPSI Disease Related Symptoms – Emotional (DRS-E)
 - FPSI Treatment Side Effects (TSE)
 - FPSI Function/Well Being (F/WB)
- Time to increase in physical symptoms of disease based on FPSI-DRS-P
- BPI-SF subscale scores and aggregate indices
 - BPI-SF Pain Severity Index
 - BPI-SF Function Interference Index
- Average Pain Score (APS)

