6.2.3.1.1 Exploratory endpoints

For all exploratory time-to-event endpoints, randomization baseline will be used for all the analyses unless otherwise specified. Week 24 baseline will not be defined for exploratory endpoints.

Radiological endpoints

Only central reviewer assessments will be analyzed for exploratory radiological endpoints.

Time to radiological bone progression is defined for each comparison as the time (days) from randomization date to the date of confirmed radiological bone progression. See [Table 9–5](#) in Appendix [9.1.4](#) for detailed censoring rules.

Time to radiological soft-tissue progression is defined as the time (days) from randomization date to the date of radiological soft tissue progression. See [Table 9–5](#) in Appendix [9.1.4](#) for detailed censoring rules.

Quantitated bone scan endpoints

Digitized images of whole body quantified technetium-99 bone scans will be evaluated by the central imaging reviewer using CAD system software using the method of Brown et al. (2012) [8], as described in the imaging charter. The central reviewer will use the CAD system software to evaluate each subject’s digitized whole body quantified technetium-99 scans at each timepoint. The reviewer will identify the bone pixels, and determine the area (cm²) and disease status (bone lesion, not bone lesion) associated with each bone pixel [8].

The analysis timepoints for the analysis of quantitative bone scan endpoints are randomization baseline, Week 8, 16, 24, and every 12 weeks thereafter.

For analyses reported by visit, nominal visit per CRF will be used.

Patient bone scan lesion area (BSLA) is defined for each subject at each assessment as the sum of the pixel areas (cm²) of the set of the whole body quantified technetium-99 bone scan imaging pixels identified as bone lesion, as determined by the central imaging reviewer using the CAD system software.

Patient bone scan timepoint response rate (week 8, 16 and week 24) For each comparison, patient bone scan timepoint response with respect to the randomization baseline will be assessed according to the following criteria in [Table 6–2](#):

Table 6–2 Patient Bone Scan Timepoint Response Criteria Following Randomization

Responder (R)	30% or greater resolution of the BSLA compared to baseline
Stable Disease (SD)	Not meeting the criteria for R, PD, or UE

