9.1.4 Censoring rules for time to radiological progression

Note: ‘radiological’ in the tables refer to either ‘radiological soft tissue’ or ‘radiological bone’ as applicable to the endpoint.

Refer to Section 4.5.2 for pooling cut-off date.

Table 9–5 applies to:

- **Time to radiological progression following randomization**
- **Time to radiological bone progression following randomization and**
- **Time to radiological soft tissue progression following randomization.**

The following censoring rules will be used for both Comparison 1 and Comparison 2. Randomization baseline is used for all comparisons.

Table 9–5 Censoring for Time to Radiological Bone/Soft Tissue Progression following randomization

Situation	End Date	Censored	Reason for Censoring
No randomization baseline or post-randomization baseline radiological assessment	Date of randomization	Yes	No baseline or post-baseline assessment.
Subject died without prior radiological progression	Date of last radiological assessment before death	Yes	No progression before death or database cutoff
Subject survived without radiological progression as of database cutoff date	Date of last radiological assessment before data cutoff	Yes	Alive and no progression before database cutoff
Subject had a radiological assessment of PD (no two consecutive missed radiological assessments*)	Date of first PD	No	N/A
PD immediately after two or more consecutive missed radiological assessments*	Date of last radiological assessment before missed assessments	Yes	Missed two or more consecutive tumor assessments
Subject discontinuation from study for reasons other than PD	Last radiological assessment date	Yes	Subject discontinued from study due to a reason other than PD
Subjects discontinued from study due to PD, but no documented date of PD	Date of last radiological assessment	Yes	Subjects discontinued from study due to PD, but no documented date of PD
New non-protocol permitted systemic anti-cancer treatment started	Date of last radiological assessment before starting new systemic anti-cancer treatment	Yes	New anti-cancer treatment started

*Two consecutive missing radiological assessments are defined as the time interval between two consecutive radiological assessments is more than 28 weeks = $2 \times (12+2)$ week, where 12-week is scheduled frequency for tumor assessment and 2-week is protocol-allowed window.

Duration = End date – randomization date +1

There will be no Week 24 baseline censoring for Comparison 2.

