In addition to the rules in [Table 9–5](#) the following rule will be applied to Comparison 1:

Situation	End Date	Censored	Reason for Censoring
Arm C subject with no radiological progression event on or after pooling cutoff date	Last radiological progression assessment on or before pooling cutoff date	Yes	Post Week 24 Arm C events censored at pooling cutoff date

When determining time to radiographic progression, the following rules will be applied by taking into consideration of both bone and non-bone disease status:

Table 9–6 Censoring for Time to Radiological Progression Following Randomization

Situation		Event/Censor	Event/censor date	Combined Non-bone and Bone outcome
1	Bone	Event (PD)	Bone scan date	Event at min(Bone scan date, Non-Bone assessment date)Event at min(Bone scan date, Non-Bone assessment)
	Non-Bone	Event (PD)	Non-Bone assessment date	
2	Bone	Censor	Bone scan date	Censor at min(Non-Bone assessment date, Bone scan date)
	Non-Bone	Censor	Non-Bone assessment date	
3	Bone	Censor	Bone scan date	Event at Non-Bone assessment date: if Non-Bone assessment date \leq Bone scan date ; Else if Non-Bone assessment date $>$ Bone scan date AND Difference $<$ 28weeks; Else censor at bone scan Date; Event at Non-Bone assessment Date: if Non-Bone assessment Date \leq Bone scan date Else if Non-Bone assessment Date $>$ Bone scan date AND Difference $<$ 28weeks Else censor at bscan Date
	Non-Bone	Event(PD)	Non-Bone assessment date	
4	Bone	Event(PD)	Bone scan date	Event at bone scan date: if Bone scan date \leq Non-Bone assessment date Else if Bone scan date $>$ Non-Bone assessment date AND Difference $<$ 28weeks; Else censor at Non-Bone assessment date
	Non-Bone	Censor	Non-Bone assessment date	

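### The 28-week gap that stands for two missed scans assumes a 12-week interval throughout, but the SAP places bone scans 8 weeks apart up to Week 24, so two missed early bone scans can go unflagged

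*SAP*

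**What the plan says.** SAP Table 9-5 (time to radiological progression, and its bone and soft-tissue versions) has a row for "PD immediately after two or more consecutive missed radiological assessments". Such a progression is censored at the last assessment before the gap. Table 9-7 has the matching row for rPFS, which also covers death. The footnote to each table supplies the definition: "Two consecutive missing radiological assessments are defined as the time interval between two consecutive radiological assessments is more than 28 weeks", computed as 2 x (12+2), "where 12-week is scheduled frequency for tumor assessment and 2-week is protocol-allowed window".

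The bone scan timepoints appear in SAP section 6.2.3.1.1, under the quantitated bone scan endpoints: "randomization baseline, Week 8, 16, 24, and every 12 weeks thereafter". Two other places agree with this schedule. Section 6.2.3.1 lists bone scan response at Weeks 8, 16 and 24. The bone progression rule in section 6.2.2.1 provides for a first scan with new lesions that "is observed < 12 weeks from randomization and is confirmed by a second bone scan taken ≥ 6 weeks later". The same section says that bone progression is judged "based on whole body technetium-99 bone scans".

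Table 9-6 also uses 28 weeks, when one modality shows progression and the other is censored. The event is kept if the two dates differ by less than 28 weeks.

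**The concern.** The footnote presents 12 weeks as the interval for the whole study. For bone scans that is true only after Week 24. A limit sized for 12-weekly scanning is too long for 8-weekly scanning, so two missed bone scans in the first 24 weeks can pass as acceptable follow-up. The next progression then counts as an event on the date it was found, whereas two scans missed later in the study lead to censoring.

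Time to radiological progression and rPFS are formally tested at one-sided 0.10 in both comparisons (SAP section 6.2.2.2). The limit helps decide which progressions count in those tests, and its stated input does not match the bone scan schedule given elsewhere in the same document.

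**Working it through.** **Inputs.** From the SAP: a flag when the gap exceeds 28 weeks; a 2-week window; bone scans at Weeks 0, 8, 16, 24, 36, 48, 60 and so on. Assumptions: the window is 2 weeks either side of each post-baseline scan, and the baseline scan falls at randomization.

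**The plan's own figure.** 2 x (12+2) = 28 weeks is reproduced. In the 12-weekly phase it is the largest gap that a single missed scan can leave (24 + 4 = 28), and two missed scans always exceed it (36 - 4 = 32).

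**Two missed bone scans, against the 28-week limit:**

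| Missed weeks | Last and next scan | Nominal gap | Range | Flagged? |
|---|---|---|---|---|
| 8, 16 | 0, 24 | 24 | 22-26 | No |
| 16, 24 | 8, 36 | 28 | 24-32 | Not at nominal dates; about half if timing is uniform within windows |
| 24, 36 | 16, 48 | 32 | 28-36 | Yes, except at the extreme of exactly 28 |
| 36, 48 | 24, 60 | 36 | 32-40 | Yes |

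**The same formula with the interval in force:**
- Baseline to Week 24: 2 x (8+2) = 20 weeks.
- Across the change of interval: (8+2) + (12+2) = 24 weeks.
- After Week 24: 28 weeks, as now.

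A limit of more than 20 weeks catches the Week 8 and 16 case (22-26). It does not flag a single missed 8-weekly scan: missing Week 8 leaves 14-18 weeks and missing Week 16 leaves 12-20.

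**Effect on the event date.** If Weeks 8 and 16 are missed and progression is seen at Week 24, the event is dated 24 - 8 = 16 weeks after the first scan that could have shown it.

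**Sensitivity to the baseline scan date.** If that scan precedes randomization by L weeks, the gap to Week 24 is 24 + L, plus or minus 2. For L = 2 the range is 24-28 and nothing is flagged. For L = 4 it is 26-30 and about half would be flagged under uniform timing. For L = 6 the nominal gap is 30 and is flagged. The SAP does not give L.

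**The value of exactly 28 weeks.** In Tables 9-5 and 9-7 a gap of exactly 28 weeks is not above the limit, so the event stays. In Table 9-6 a difference of exactly 28 weeks is not below the limit, so the subject is censored. The nominal distance from Week 8 to Week 36 is exactly 28 weeks.

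**The case against.** The strongest reply is that a single elapsed-time limit is explicit, reproducible and the same for all arms. One missed scan in the 12-weekly phase leaves 20 to 28 weeks, and a progression after it is kept. Two missed scans at Weeks 8 and 16 leave about 24 weeks, so the uncertainty about the date is similar. That would be a sound defence of a rule stated as an elapsed-time limit. The SAP instead states a rule about missed assessments and derives the limit from a schedule that does not hold for early bone scans.

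Several stronger readings are tempting and are not supported:
- That the tables contradict themselves. They do not: the row is defined by its footnote, and a 24-week gap does not meet that definition. The error is in the footnote's input.
- That all tumor imaging is 8-weekly at first. The SAP gives that schedule only for bone scans. Section 3.2 leaves the full schedule to the protocol, which is not at hand, so no defect is shown for soft-tissue progression.
- That two early missed scans can never be flagged. This depends on the baseline scan date, as shown above.
- That progressions are dated 24 weeks late. That is an upper bound measured from randomization; against the missed Week 8 scan the delay is 16 weeks.
- That early deaths in rPFS are generally mishandled. Table 9-7 separately counts a death before the first radiological assessment as an event.
- That the 28 weeks in Table 9-6 is wrong for the same reason. It compares dates across modalities and cannot be judged without the CT/MRI schedule.

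**Conclusion.** The point holds for bone progression and for the bone component of time to radiological progression and rPFS. On the SAP's own bone scan schedule, missing Weeks 8 and 16 goes unflagged when the baseline scan is at or shortly before randomization. Missing Weeks 16 and 24 is flagged only when visits run late. Two missed scans in the 12-weekly phase are flagged as intended.

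The consequence is limited. The primary endpoint, SSE-FS, has its own 13-week rule and is untouched. The SAP does not say how often two early scans are missed, so the number of subjects cannot be derived; it is probably small. A reader might infer that one arm is favored, but nothing in the SAP establishes a direction. The correction is still worth making, because a wrong input enters formally tested secondary endpoints and is easy to put right.

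**What to change.** In Tables 9-5 and 9-7, define the condition by counting: two or more scheduled assessments in a row, for the relevant modality, with no scan in window. If a gap is preferred, derive it from the schedule in force. For bone this is 20 weeks up to Week 24, 24 weeks across the change of interval and 28 weeks afterwards. When the last scan is the baseline scan, count from randomization. Otherwise a scan done 4 weeks before randomization would make a single missed Week 8 scan look like a gap of 16 + 4, plus or minus 2, that is 18-22 weeks, which can exceed 20.

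Check the 28 weeks in Table 9-6 against the protocol's bone and CT/MRI schedules, and use the same inequality in all three tables so that exactly 28 weeks is handled one way.

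The cost is revised SAP wording and a few lines of derivation code. The statistical downside is that a few documented early progressions would be censored at or near baseline, adding almost no follow-up, and such censoring may be informative. Keeping the present 28-week rule as a sensitivity analysis would show whether the choice matters.

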4.5 Data Rules

4.5.1 Determining Baseline Values

This study has two distinct baselines for efficacy analyses, the randomization baseline and the Week 24 baseline.

Randomization baseline value for efficacy parameters: is defined as the last non-missing value on or before the date of randomization.

Week 24 baseline: Unless otherwise specified, the ‘Week 24 baseline’ is defined as the date of the 6th injection. This baseline is defined only for those subjects who are eligible for Comparison 2 analyses. That is, subjects who had received at least 6 injections.

Week 24 baseline value for efficacy parameters: Unless otherwise specified, the ‘Week 24 baseline value’ is defined as the last non-missing value on or before the date of the 6th injection.

Ideally, this visit would be the date of the 7th injection for Arm C subjects and expected 7th injection date for Arm A subjects. However, the end of treatment visit (30±7 days from last dose) for Arm A subjects could be missing due to consent withdrawal or happen out of visit window. Hence, there is no comparable visit for Arm A subjects that could be used as the expected 7th injection date.

To account for this and achieve comparability between the two arms, the 6th injection date is used as the reference date for Comparison 2 subjects. It should be noted that this could lead to a somewhat dilution of the treatment effect in Arm C due to an early reference date.

Baseline value for safety parameters: is defined as the last non-missing value on or before the date of first dose.

4.5.2 Pooling cut-off date for Arm C subjects in Comparison 1

For Comparison 1, Arm C subjects are planned to be pooled with Arm A subjects. This pooling will be done such a way that only comparable data from Arm C subject pooled. The following algorithm will be used to identify the cut-off date for pooling:

Arm C: Pooling cut-off date = $7*28 + \text{randomization date}$; for subjects that were randomized but not treated,
= $(7-x)*28 + \text{last dose date}$; for $1 \leq x \leq 6$,
= 7th dose date; for $x \geq 7$,
where x be the number of injections received.

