9.1 Censoring Rules

9.1.1 Censoring rules for Symptomatic Skeletal Event-Free Survival (SSE-FS)

Comparison 1:

- Arm C subjects who had SSE assessments or SSE event or death (in the absence of an SSE event) after ‘pooling cut-off date’ will be censored on last SSE assessment date prior to ‘pooling cut-off date’. Refer to Section 4.5 for pooling cut-off date.
- All other subjects in arms A, B and C, refer to [Table 9–1](#) for censoring rules.
- Symptomatic Skeletal Event Free Survival (SSE-FS) following randomization = End Date – Date of Randomization +1

Table 9–1 Comparison 1: Censoring for Symptomatic Skeletal Event Free Survival (SSE-FS)

Situation	End Date	Censored	Reason for Censoring
No post-randomization SSE assessment and no death	Date of Randomization	Yes	No post-baseline SSE assessments and no death
Subject had a SSE event	Date of first SSE	No*	N/A
Death without prior SSE (<13 weeks between last SSE assessment and death) #	Date of Death	No*	N/A
Death without prior SSE (≥ 13 weeks between last SSE assessment and death) #	Last SSE assessment before the missing SSE assessments#	Yes	≥ 13 weeks between last SSE assessment and death
Neither SSE nor Death by database cutoff date	Last SSE assessment prior to database cutoff	Yes	Neither SSE nor death

*The earliest end date in the table is used in calculating the SSE-FS.

#: use randomization date instead of last SSE assessment date if no post-randomization SSE assessment.

Note: symptomatic skeletal events immediately after missing SSE assessments are still counted as events in the analysis of SSE-FS.

Comparison 2:

- All subjects eligible for Comparison 2, refer to [Table 9–2](#) for censoring rules.
- Symptomatic Skeletal Event Free Survival (SSE-FS) following Week 24 baseline= End Date – Date of Week 24 baseline(the 6th dose date) +1

Table 9–2 Comparison 2: Censoring for Symptomatic Skeletal Event Free Survival (SSE-FS)

Situation	End Date	Censored	Reason for Censoring
No SSE assessment or death following Week 24 baseline	Date of Week 24 baseline	Yes	No post-Week 24 baseline SSE assessments and no

			death.
Had an SSE event between date of randomization and Week 24 baseline	Date of Week 24 baseline	Yes	First event occurred between date of randomization and Week 24 baseline
Subject had a SSE event after Week 24 baseline	Date of first SSE	No*	N/A
Death without prior SSE (<13 weeks between last SSE assessment and death) #	Date of Death	No*	N/A

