Arm C subject with no death or radiological progression event on or after pooling cutoff date	Last radiological progression assessment on or before pooling cutoff date	Yes	Post Week 24 Arm C events censored at pooling cutoff date

Title page

A three arm randomized, open-label Phase II study of radium-223 dichloride 50 kBq/kg (55 kBq/kg after implementation of NIST update) versus 80 kBq/kg (88 kBq/kg after implementation of NIST update) , and versus 50 kBq/kg (55 kBq/kg after implementation of NIST update) in an extended dosing schedule in subjects with castration-resistant prostate cancer metastatic to the bone

[Standard dose versus high dose and versus extended standard dose radium-223 dichloride in castration-resistant prostate cancer metastatic to the bone]

Bayer study drug BAY 88-8223 / Radium-223 dichloride / Xofigo

[Study purpose:] Efficacy, dose-finding

Clinical study phase: II **Date:** 02 July 2018

Study No.: BAY 88-8223 / 16507 **Version:** 1.0

Author: PPD

Confidential
The information provided in this document is strictly confidential and is intended solely for the guidance of the clinical investigation. Reproduction or disclosure of this document, whether in part or in full, to parties not associated with the clinical investigation or its use for any other purpose without the prior written consent of the sponsor is not permitted.

Throughout this document, symbols indicating proprietary names (®, TM) are not displayed. Hence, the appearance of product names without these symbols does not imply that these names are not protected.

This Statistical Analysis Plan is produced on a word-processing system and bears no signatures.
The approval of the Statistical Analysis Plan is documented in a separate Signature Document.

Table of Contents

Title page.....	1
Abbreviations.....	2
1. Introduction.....	2
2. Study Objectives.....	2
3. Study Design.....	4
4. General Statistical Considerations.....	4
5. Analysis Sets.....	4
6. Statistical Methodology.....	4
6.1 Population characteristics.....	4
6.1.1 Additional Summary of Baseline Characteristics.....	4
6.1.2 Additional Summary of Prior/Concomitant Bone Health Agent (BHA) use.....	4
6.2 Efficacy.....	4
6.3 Exploratory variables and analyses.....	5
6.4 Pharmacokinetics.....	5
6.5 Safety.....	5
6.5.1 Adverse Events.....	5
7. Document history and changes in the planned statistical analysis.....	5
8. References.....	5

Abbreviations

AE	Adverse event
BHA	Bone health agent
CI	Confidence interval

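### The Comparison 1 pooling rows for radiological progression and rPFS select the wrong Arm C subjects: the condition reads on or after the cut-off where the stated reason requires on or before

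*SAP*

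**What the plan says.** Section 4.5.2 defines an Arm C pooling cut-off date so that "only comparable data from Arm C subject pooled". For subjects with seven or more injections it is the date of the seventh dose.

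For the two radiological endpoints the cut-off is applied by one extra row under each main censoring table. Each row is introduced as applying "In addition to the rules in" the main table.

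- **Time to radiological progression (9.1.4).** Situation: "Arm C subject with no radiological progression event on or after pooling cutoff date". End date: "Last radiological progression assessment on or before pooling cutoff date". Censored: yes. Reason: "Post Week 24 Arm C events censored at pooling cutoff date".
- **rPFS (9.1.5).** Situation: "Arm C subject with no death or radiological progression event on or after pooling cutoff date", with the same end date and reason.

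Table 9-5 separately counts progression as an event at its first date: "Subject had a radiological assessment of PD (no two consecutive missed radiological assessments" and so on, not censored. Table 9-7 has the equivalent rows for progression and death.

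Section 6.2.2.2 tests both endpoints in Comparison 1 at a one-sided 0.10. Table 9-5 also governs the exploratory times to bone and to soft-tissue progression.

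**The concern.** The situation column decides which subjects a program censors, and here it picks the wrong ones. A subject with no event on or after the cut-off has no late event to remove, so the situation and reason columns of the same row cannot both hold.

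Two kinds of Arm C subject are affected. One whose first event falls after the cut-off, possibly while on extended dosing, does not meet the row, and the main table counts the event in the standard-dose group. One who progressed before the cut-off, when Arms A and C had the same regimen, does meet the row and may be censored although the event is valid standard-dose information. At stake is whether the Comparison 1 tests of two secondary endpoints are valid.

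**Working it through.** **1. Rules side by side.**

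| SAP section | Arm C subjects cut in Comparison 1 |
|---|---|
| 9.1.1 SSE-FS | "Arm C subjects who had SSE assessments or SSE event or death (in the absence of an SSE event) after" the cut-off |
| 9.1.2 OS | died, or known alive, after the cut-off |
| 9.1.3 other time-to-event endpoints | assessed, or with an event, after the cut-off |
| 9.1.4 and 9.1.5 radiological | no event on or after the cut-off |

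Only the last line selects the opposite group. Tables 9-5, 9-6 and 9-7 hold no other Arm C cut-off rule, and the two supplements refer back to the main SAP for these endpoints.

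**2. The added row applied to each type of Arm C subject.**

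| Arm C subject | Meets added row? | Meets an event row? | Outcome as written | Intended |
|---|---|---|---|---|
| First event after cut-off | No | Yes | Event counted | Censored |
| Progression before cut-off, nothing later | Yes | Yes | Undecided: no precedence stated | Event |
| rPFS only: early progression, death after cut-off | No | Yes | Early event counted | Event |
| No event | Yes | No | Censored by the cut-off | Censored by the cut-off |

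The first line holds on any reading. The second depends on which row wins.

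**3. Illustration of size.** The SAP gives no radiological median and no figure for these endpoints, so there is nothing to reproduce.

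- From Section 3.4: 360 subjects at 1:1:1 (120 per arm), 3% loss per month, 16 months of accrual, analysis at 39.1 months.
- Assumed: exponential times, a radiological median of 6, 9 or 12 months, a cut-off at 24 weeks (24 × 7 / 30.4375 = 5.52 months), an unstratified log-rank test, and events dated when they occur.

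Expected Arm C events before the cut-off are 120 × λ/(λ+μ) × [1 − exp(−5.52(λ+μ))], with λ = ln 2/median and μ = −ln 0.97 = 0.0305. For a median of 9 months, λ = 0.0770 and λ+μ = 0.1075, so 120 × 0.717 × (1 − 0.553) = 38. Medians of 6 and 12 months give about 53 and 30. In simulation, about 41 to 44 Arm C events fall after the cut-off.

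Simulated hazard ratio (high/standard) with no true difference:

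| Reading | 6 months | 9 months | 12 months |
|---|---|---|---|
| Intended rule | 1.00 | 1.00 | 1.00 |
| Added row overrides (early events lost, late kept) | 1.29 | 1.13 | 1.02 |
| Progression row prevails (early and late kept) | 0.94 | 0.88 | 0.83 |

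Under the last reading, one-sided rejection in favour of high dose is about 24%, 36% and 50% instead of 10%. A repeat run agreed to within about 0.01 on the hazard ratio and 1 to 2 percentage points on rejection.

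The direction changes for a clear reason. Event-free Arm C subjects leave at the cut-off under either reading, while those who later progress stay. After the cut-off, Arm C therefore consists only of subjects who will have an event, which inflates the standard-dose hazard. Deleting the early Arm C events pulls the other way, and outweighs it most clearly at short medians.

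Modelling matters too. If progression is recorded only at scans in Weeks 8, 16, 24 and every 12 weeks after (the quantitative bone-scan timepoints), the override reading gives 1.43, 1.19 and 1.05.

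**The case against.** The strongest defence is that the reason column makes the intent plain. This looks like a drafting slip, and a careful programmer would query it or code the intended rule. The endpoints are secondary or exploratory, and the Arm A versus Arm B sensitivity analysis in Section 6.2, which leaves out Arm C, would show a distortion. All of this stands and limits the consequences. It does not repair the row: nothing else in 9.1.4 or 9.1.5 censors late Arm C events for these endpoints.

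A reader might go further and infer that every Arm C event before the cut-off is erased, so that the bias necessarily runs against the high dose. The SAP does not support that, for two reasons.

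- The added row supplements the main table without stated precedence, and an early progression also satisfies the row that counts it as an event. If that row prevails, the bias runs in favour of the high dose.
- For rPFS, an early progression followed by a death on or after the cut-off fails the added row and remains an event. Assuming a median of 12 months from progression to death, about 33 of 53, 25 of 38 and 20 of 30 early events escape in this way (progression medians of 6, 9 and 12 months). The null hazard ratio is then about 1.04, 0.95 and 0.89.

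A large loss of power is likewise tied to one case. With a true hazard ratio of 0.667 and the added row overriding, power falls from about 95% to 58% at a median of 6 months, but is nearly unchanged at 12 months.

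**Conclusion.** The error is real and should be corrected before the analysis. In both added rows the condition is inverted relative to the row's own reason, to Section 4.5.2 and to the parallel rules. Retention of late Arm C events in the standard-dose group follows on any literal reading. Loss of early ones follows only if the added row overrides, and for rPFS only where no death occurs on or after the cut-off.

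The analyses affected are the Comparison 1 analyses of time to radiological progression and rPFS, and of the exploratory bone and soft-tissue progression times. SSE-FS, OS, Comparison 2 and the Arm A versus Arm B sensitivity analysis are not affected.

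No single bias figure can be given. Across the assumed medians of 6 to 12 months, the null hazard ratio runs from 1.29 to 1.02 under one precedence and from 0.94 to 0.83 under the other. These values illustrate the problem under assumed medians and are not predictions for this trial.

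**What to change.** 1. In both added rows, replace *on or after* with *on or before* in the situation column, and add that subjects with a later event are included. For rPFS, keep death in the condition. Leave the end date as it is.
2. State that Arm C events on or before the cut-off count under the main table, and that the added row overrides the main-table event rows for later Arm C events.
3. State that the earliest applicable censoring date is used where another censoring rule also applies (new anti-cancer therapy, missed assessments, discontinuation). Tables 9-1 and 9-2 carry an earliest-date footnote, but Tables 9-5 and 9-7 do not. Without it, the corrected row could move an already censored Arm C subject to a later date.
4. Check the analysis programs for all four radiological endpoints against the corrected rows.

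The cost is one phrase in each of two rows, a short precedence note and a program check. No data collection or sample size changes.
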